13.6.5 Electrocardiogram

All ECGs will be categorised as "normal", "abnormal, not clinically significant", or "abnormal, clinically significant" (as judged by the investigator). The assessment will be summarised by visit and time point relative to IMP administration.

All ECG data will be listed by subject.

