5.4 Exclusion Criteria

Subjects must not enter the trial if any of the following exclusion criteria are fulfilled:

Concurrent serious medical condition which in the opinion of the investigator constitutes a
risk or a contraindication for the participation in the trial or that could interfere with the trial
objectives, conduct or evaluation.

Vicore Pharma ABVersion: 2.0Trial ID: VP-C21-013Date: 03-MAR-2023

- 2) Known, active hepatitis B, C, or human immunodeficiency virus (HIV) infection (*i.e.*, HIV with a CD4 count <500 cells/mm³).
- 3) Impaired hepatic function or clinically significant liver disease, which in the investigator's opinion makes the subject inappropriate for this trial.
- 4) Severe renal impairment (*i.e.*, estimated glomerular filtration rate (eGFR) ≤30 mL/min/1.73 m²).
- 5) Prolonged QTcF (QT interval with Fridericia's correction) (>450 ms), atrial fibrillation, clinically significant arrhythmia or other clinically significant abnormality in the resting ECG at screeening (Visit 1), as judged by the investigator.
- 6) Unstable or deteriorating cardiac condition.
- 7) History of severe allergy/hypersensitivity or ongoing allergy/hypersensitivity, as judged by the investigator, or history of hypersensitivity to drugs with a similar chemical structure or class to any of the IMPs.
- 8) Pregnant or breast-feeding female subjects.
- 9) Malignancy within the past 5 years with the exception of in situ removal of basal cell carcinoma and cervical intraepithelial neoplasia grade I.
- 10) Planned major surgery within the duration of the trial.
- 11) Treatment with the medications listed below within 14 days prior to screening (Visit 1) or anticipated need for such medication during the participation in this trial:
 - Insulin.
 - Glucagon-like peptide-1 (GLP-1) agonists.
 - Strong Cytochrome P450 (CYP) 3A4 inducers (e.g., rifampicin, phenytoin, carbamazepine and St. John's Wort).
 - Strong CYP 3A4 inhibitors (*e.g.*, clarithromycin, ketoconazole, nefazodone, itraconazole, ritonavir).
 - Warfarin, digoxin and other medication where the dose needs to be individually titrated.
 - Narrow therapeutic index drugs that are substrates of CYP1A2, CYP2C8, CYP2C9, CYP2C19, CYP3A4, or OATP1B1.
- 12) Current or previous participation in any other clinical trial where the subject has received a dose of IMP within 1 month or 5 half-lives of the IMP, whichever is longest, prior to screening.

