8.3.5 Electrocardiogram

A 12-lead ECG will be recorded in supine position after 10 minutes of rest at visits specified in the flow chart for trial procedures (Table 1). At visits 2 and 3, ECGs will be recorded within 60 minutes prior to IMP dosing and again prior to initiating the EndoPAT assessment, 50±10 minutes after the IMP dosing. The ECGs will be reviewed and interpreted on-site by the investigator or designee.

Any ECG findings outside of normal ranges will be specified and documented as clinically significant or not clinically significant. The assessment and the time point of ECG collection will be recorded in the eCRF. Abnormal post-IMP administration findings assessed by the investigator as clinically significant will be reported as AEs.

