13.1 General

Continuous data will be presented in terms of evaluable and missing observations, arithmetic mean, standard deviation (SD), median, minimum, and maximum value.

Categorical data will be presented as counts and percentages. When applicable, summary data will be presented by treatment, and by assessment time. Individual subject data will be listed by subject number, treatment and, where applicable, by assessment time.

All descriptive summaries and statistical analyses will be performed using SAS Version 9.4 or later (SAS Institute, Inc., Cary, NC).

Baseline (apart from EndoPAT assessments) will be defined as the last non-missing data collection point prior to the (first) administration of IMP. All hypothesis testing will use a significance level of 5 %. No imputation of missing data will be performed.

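### The planned ECG table (three-level judgement by visit and time point) mixes C21 and placebo at each visit, and no planned summary would show a moderate in-range QTcF shift by treatment

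*Combined protocol and SAP*

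**What the plan says.** **Collection.** Section 8.3.5 states: "At visits 2 and 3, ECGs will be recorded within 60 minutes prior to IMP dosing and again prior to initiating the EndoPAT assessment". The second recording falls 50±10 minutes after dosing, and Table 1 gives the same schedule. On what is captured, Section 8.3.5 says: "The assessment and the time point of ECG collection will be recorded in the eCRF". Findings outside normal ranges are also to be specified. Numeric intervals are not named.

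**Analysis.** Section 13.6.5 sorts each ECG as normal, abnormal but not clinically significant, or abnormal and clinically significant, on the investigator's judgement. It continues: "The assessment will be summarised by visit and time point relative to IMP administration", and adds: "All ECG data will be listed by subject". It names no QTcF summary, no change from pre-dose, no outlier count and no split by treatment.

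**General rules.** Section 13.1 has summary data shown by treatment and assessment time where applicable. The Protocol Summary has both quantitative and qualitative variables summarised by assigned treatment and time point. Section 13.1 also states: "Baseline (apart from EndoPAT assessments) will be defined as the last non-missing data collection point prior to the (first) administration of IMP".

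**QTcF elsewhere.** The only QTcF figure is the screening exclusion above 450 ms (Section 5.4, criterion 5).

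**The concern.** Safety is in the trial title and among the secondary objectives, and the protocol screens on QTcF. The schedule yields a same-day pre/post pair on each treatment in the same person, which is the comparison a crossover exists to provide. The section that governs ECG reporting then drops two things.

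- **Treatment.** The table is split by visit and time point. Pre-dose and post-dose judgements are therefore shown separately, but C21 and placebo are not.
- **Magnitude.** A three-level judgement does not register movement inside the normal range.

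What is at stake is modest but real: the trial is meant to inform later trials, and it could finish without a tabulated description of what C21 does to QTcF relative to placebo.

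**Working it through.** The documents give no ECG sample-size figure, QTcF mean or QTcF SD, so there is no stated figure to reproduce. Step 1 is a reading of the text; steps 2 to 4 are illustrations on stated assumptions.

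**1. The rules side by side.** Section 13.6.5 names visit and time point. Section 13.1 (when applicable) and the Protocol Summary name treatment and time point. Section 13.6.1 shows that the plan can name treatment explicitly for a safety table, since it does so for adverse events. The ECG section is not reconciled with the general rules. Even if the general rules prevail, they yield a by-treatment table of categories. A quantitative QTcF summary would need a numeric variable that no section names for capture.

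**2. What pooling by visit does.** Section 7.3 gives random order; the sequence ratio is not stated. Assume 6 subjects per sequence at the target of 12 (Section 6.2) and a mean shift *d* on C21 only. Each visit's post-dose group then has 6 subjects on C21 and 6 on placebo:

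- mean shift at each visit = (6/12) × *d*; for *d* = 10 ms this is 5 ms at Visit 2 and 5 ms at Visit 3;
- expected between-visit contrast = 5 − 5 = 0 ms;
- by-treatment contrast = 10 ms.

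The same halving applies to the proportion of subjects whose category changes because of C21.

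**3. Whether a threshold-type judgement would react.** Assume that pre-dose QTcF is normal with SD 15 ms, truncated at 450 ms; that residual change has SD 8 ms; and that 450 ms stands in for the upper limit of normal. The protocol does not define normal this way. A simulation of 2,000,000 draws per mean gives the probability *p* that a post-dose value exceeds 450 ms. The chance that none of 12 subjects exceeds it on C21 is (1 − *p*)^12.

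| Mean pre-dose QTcF | No shift | 10 ms shift | 20 ms shift |
|---|---|---|---|
| 400 ms | 98% | 90% (*p* = 0.0089) | 63% (*p* = 0.0383) |
| 410 ms | 92% | 65% (*p* = 0.0352) | 23% (*p* = 0.1163) |
| 420 ms | 76% | 28% (*p* = 0.1003) | 3% (*p* = 0.2619) |

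A moderate shift can leave such a judgement unchanged. A larger shift in subjects near the limit would usually move at least one of them.

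**4. What the within-subject contrast could deliver.** Take the C21-minus-placebo difference in (post-dose − same-visit pre-dose) QTcF, adjusted for period, with n − 2 degrees of freedom and balanced sequences:

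90% CI half-width = t(0.95, n − 2) × SD / √n

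At n = 12 this is 1.812 × SD / 3.464 = 0.523 × SD.

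| Assumed SD of the difference | Half-width, n = 12 | Power for 10 ms, two-sided 10% level |
|---|---|---|
| 8 ms | 4.2 ms | 0.99 |
| 12 ms | 6.3 ms | 0.85 |
| 16 ms | 8.4 ms | 0.65 |

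At SD 12 ms the half-width is 7.1 ms for n = 10 and 5.7 ms for n = 14. The contrast combines four ECGs. With independent errors its SD is √4 = 2 times the single-reading SD, so 8 to 16 ms corresponds to 4 to 8 ms per reading.

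**The case against.** The strongest reply is that the plan has more protection than Section 13.6.5 alone suggests.

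- **By-treatment rules exist.** This stands in part. They show that the by-visit table may not be the whole intention, but they conflict with the specific section rather than settle it, and they do not create a QTcF variable.
- **Nothing marked would be missed.** A reader might infer that QTcF prolongation on C21 could go entirely unseen. The documents do not support that. Every ECG is reviewed on site, clinically significant post-dose findings become adverse events, treatment-emergent events are tabulated by treatment, and ECG data are listed for only 10 to 14 subjects. These routes do not cover a moderate shift within the normal range, and the listings may not hold in-range QTcF values if those are not entered.
- **The baseline rule is harmless as it stands.** A reader might infer that Section 13.1 already makes Visit 3 ECG changes wrong. It does not, because no ECG change from baseline is planned. The point is preventive: if a change analysis were added under that rule, Visit 3 would be compared with an ECG from before the first dose, and its own pre-dose ECG would be ignored.
- **450 ms is a screening limit.** This stands. One cannot say that a rise from 400 to 445 ms must be judged normal both times, only that it could be.
- **A separate SAP may add detail.** Section 13 defers technical detail to one, and its text is not in the document reviewed. This limits the conclusion to what the protocol specifies. A later SAP still cannot summarise values that the eCRF did not capture.
- **A QTcF confidence interval is more than a 12-subject pharmacodynamic trial needs.** This is fair. A descriptive summary closes the gap; the interval is optional.

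**Conclusion.** The point holds in a limited form. As written, Section 13.6.5 gives a table that cannot attribute an ECG effect to C21 and is not reconciled with the general by-treatment rules. No planned summary would show a moderate, in-range QTcF shift by treatment.

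The mixing of treatments within visits follows from the design. The exact halving (10 ms seen as 5 ms at both visits) rests on a 6/6 split. The 28% to 90% chance that a 10 ms shift takes no subject above 450 ms rests on assumed means of 420 down to 400 ms, the assumed SDs, and 450 ms as a stand-in for the normal limit. The precision of a within-subject estimate cannot be stated from the documents; about 4 to 8 ms at n = 12 is a range over assumed SDs of 8 to 16 ms. This is a worthwhile, low-cost improvement to safety reporting. It does not affect the primary analysis, and it does not show that subjects are left unmonitored.

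**What to change.** 1. **Section 13.6.5, category table.** Summarise the three-level assessment by treatment received and time point relative to dosing, and align the section with Section 13.1 and the Protocol Summary. A by-visit version may be kept alongside.
2. **Section 8.3.5 and the eCRF.** State that the numeric QTcF value is recorded for every ECG, including those judged normal.
3. **Section 13.6.5, QTcF.** Add, for example: *QTcF and its change from the pre-dose to the post-dose ECG of the same visit will be summarised descriptively by treatment received, with the number of subjects with QTcF above 450 ms at each time point.*
4. **Section 13.1.** State that for this change the baseline is the pre-dose ECG of the same visit.
5. **Optional.** Report the within-subject C21-minus-placebo difference in QTcF change with a 90% CI, labelled descriptive.

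The cost is some eCRF fields, the associated data entry and a few tables. No extra ECGs or visits are needed. The eCRF change should be made before the first subject is dosed, or the values entered from the stored tracings if recruitment has begun.

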13.6.6 Laboratory Safety Assessments

All clinical laboratory values outside of normal ranges will be categorised as "abnormal, not clinically significant", or "abnormal, clinically significant" as judged by the investigator.

All clinical laboratory data (i.e., values outside of normal ranges and categorisation) will be listed by subject.

Clinical Trial Protocol

Vicore Pharma AB Version: 2.0 Trial ID: VP-C21-013 Date: 03-MAR-2023

14 GOOD CLINICAL PRACTICE

This trial will be carried out in compliance with the protocol, current ICH GCP, standard operating procedures, the EU Clinical Trials Directive (2001/20/EC), and applicable local regulatory requirements.

The investigator agrees, when signing this protocol, to adhere to the instructions and procedures described in it, to the principles of the Declaration of Helsinki, current ICH GCP, and applicable regulatory requirements.

In compliance with ICH GCP R2 requirements, sponsor will identify those processes and data that are critical to ensure human subject protection and the reliability of trial results and furthermore, identify, evaluate, control, communicate and review risks to those.

15 ETHICS

15.1 Independent Ethics Committees / Health Authorities

Before implementing this trial, the protocol, the proposed subject information and subject consent form, and other documents as required, will be reviewed by properly constituted Independent Ethics Committees (IECs) and by the national regulatory authorities.

A signed and dated statement that the protocol and subject information and subject consent form have been approved by the IECs and regulatory authorities will be obtained before trial initiation.

For each individual IEC the name and occupation of the chairman and the members of the IEC will be collected as well as a statement that the IEC works in accordance with ICH GCP.

IECs will receive updates on trial progress according to local regulations.

15.2 Informed Consent

The subject's signed and dated informed consent to participate in the trial will be obtained prior to any trial related procedure being carried out.

Before any trial related procedure the investigator will explain to the potential subject the aims, methods, reasonably expected benefits and potential hazards of the trial and any discomfort participation in the trial may entail. Subjects will be informed that participation in the trial is voluntary and that the subject may withdraw from the trial at any time and for any reason. Subjects will be informed that if they choose not to participate, this will not affect the care the subject will receive for the treatment of his or her disease. Finally, subjects will be informed that their records may be accessed by health authorities and authorized sponsor staff without violating the confidentiality of the subject, to the extent permitted by the applicable laws or regulations.

All subjects will be given opportunity to ask questions and will be given sufficient time to consider before consenting. The subjects may choose to be accompanied, *e.g.* by a family member, during the information process. After having consented, a copy of the informed consent form will be given to the subject.

Clinical Trial Protocol

Vicore Pharma AB Version: 2.0 Trial ID: VP-C21-013 Date: 03-MAR-2023

15.3 Subject Information Card

The subject will be provided with a subject information card including the following information:

- That they are participating in a clinical trial.
- Subject trial ID.
- That they are treated with the IMP.
- The name and phone number of the investigator.
- The name and address of the sponsor.

15.4 Subject Privacy and Data Protection

The informed consent includes information that data will be recorded, collected, and processed and information related to potential transfer to European Economic Area (EEA) or non-EEA countries. In accordance with the General Data Protection Regulation (GDPR [EU] 2016/679), these pseudonymised data will not identify any subjects taking part in the trial. If any part of the data is handled by any other organisation, inside or outside the European Union, appropriate agreements and/or other documentation will be established, to ensure that the data processing is performed in accordance with the provisions of the GDPR and other relevant legislation before any data transfer takes place.

The subject has the right to request access to their personal data and the right to request rectification of any data that is not correct and/or complete in accordance with GDPR and the request will be raised to the PI.

The investigator must file a subject identification list which includes sufficient information to link records, i.e., the eCRF and clinical records. This list must be preserved for possible future inspections/audits but must not be made available to the sponsor except for monitoring or auditing purposes.

Personal data that are collected in the trial such as health information and ethnicity are considered as sensitive personal data. This data will be pseudonymized, i.e., personally identifiable information (PII) will be removed and replaced by a unique subject ID and will be processed by the sponsor and other involved parties during the trial. After the trial end, only pseudonymized data can be used, i.e., aggregated data sets, can be used.

For this trial, the sponsor is the data controller of all data processed during the trial (e.g., trial master file [TMF], trial reports) and any subcontractors used in the trial are data processors.

For data that are processed at the trial site (e.g., medical records and ISF), the site is the data controller.

16 AUDITS AND INSPECTIONS

A representative of the sponsor may visit the trial site(s) at any time during the trial or after completion of the trial to conduct an audit of the trial. These audits will require access to all trial records, including source documents, for inspection and comparison with the eCRFs. The

Clinical Trial Protocol

Vicore Pharma AB Version: 2.0 Trial ID: VP-C21-013 Date: 03-MAR-2023

investigator and other trial personnel will be responsible for being present and available for consultation during routinely scheduled site audit visits conducted by the sponsor's representative.

Similar auditing procedures (inspections) may also be conducted by agents of regulatory health authorities, either as part of a national GCP compliance program or to review the results of this trial in support of a regulatory submission. The investigator should notify the sponsor's representative or sponsor immediately, if he/she has been contacted by a regulatory agency concerning an upcoming inspection.

17 MONITORING

Monitoring will be conducted by a sponsor representative. Before trial initiation the monitor will review the protocol and the eCRF with the investigator(s) and their trial personnel.

As described in the monitoring plan, the monitor will periodically visit the trial site to check the completeness of subject records, the accuracy of entries in eCRFs, the adherence to the protocol and to GCP, the progress of enrolment and the handling and accounting of IMP. Key trial personnel must be available to assist the monitor during these visits.

The investigator must give the monitor direct access to source data/documents (e.g. relevant hospital or medical records) to confirm their consistency with the entries in eCRFs. No information in these records about the identity of the subjects must leave the trial site.

18 REPORTING OF RESULTS

18.1 Clinical Trial Report

Data will be reported in an integrated clinical trial report in compliance with the requirements of the current version of ICH E3: Structure and Content of Clinical Study Report. The signatory investigator will review and sign the integrated clinical trial report.

18.2 Use of Information

All unpublished information relating to this trial and/or to the trial drug is considered confidential by the sponsor and shall remain the sole property of the sponsor.

The investigator must accept that the sponsor may use the information from this clinical trial in connection with the development of the IMP, and therefore, may disclose it as required to other investigators, to government licensing authorities, to regulatory agencies of other governments, stock exchange market, and commercial partners.

18.3 Publication of Results

The sponsor is committed to publishing the trial results, whether positive or negative, in a peer-reviewed journal.

Clinical Trial Protocol

Vicore Pharma AB Version: 2.0 Trial ID: VP-C21-013 Date: 03-MAR-2023

The criteria for authorship as set out by the Committee of Medical Journal Editors (www.icmje.org) will be applied (Wager et al., 2003; Graf et al., 2009).

The contributorship model will be applied and contributors who do not meet the criteria for authorship will be listed in an acknowledgments section with descriptions of the role of each contributor in order to ensure indexation in the National Library of Medicine.

Publications are subject to the following conditions:

- Data are the property of the sponsor and cannot be published without prior authorization from the sponsor.
- Publications should be drafted with protection of individual privacy, intellectual property and contract rights in mind, and also conform to legislation and current national practices in patent and other laws.
- The primary publication (*i.e.* the results from all centers) should be published before, or in parallel with, any secondary publications.
- Publications shall not disclose any sponsor confidential information or property.

19 INSURANCE AND LIABILITY

The sponsor has subscribed to an insurance policy covering, in its terms and provision, its legal liability for injuries caused to participating subjects and arising out of trial procedures performed in accordance this protocol, in accordance with applicable law and with ICH GCP R2.

Clinical Trial Protocol

Vicore Pharma AB Version: 2.0 Trial ID: VP-C21-013 Date: 03-MAR-2023

21 ABBREVIATIONS

Abbreviation	Explanation
ADR	Adverse Drug Reaction
AE	Adverse Event
AI	Augmentation Index
ALP	Alkaline Phosphatase
ALT	Alanine Aminotransferase
ANC	Absolute Neutrophil Count
ANOVA	Analysis of Variance
ARB	Angiotensin Receptor Blocker
AST	Aspartate Aminotransferase
AT1R	Angiotensin II Type 1 Receptor
AT2R	Angiotensin II Type 2 Receptor
ATC	Anatomical Therapeutic Chemical
ATRAG	Angiotensin II Type 2 Receptor Agonist
AUC	Area Under the Curve
AV	Atrioventricular
BID	Twice daily (lat. bis in die)
BMI	Body Mass Index
BCRP	Breast cancer resistance protein
BUN	Blood Urea Nitrogen
C21	Compound 21
Cmax	Maximum plasma concentration
COVID-19	Coronavirus Disease 2019
CNS	Central Nervous System
CRF	Case Report Form
CRP	C-reactive protein
CTCAE	Common terminology criteria for adverse events
CTP	Clinical Trial Protocol
CTR	Clinical Trial Report
CV	Coefficient of Variation
CYP	Cytochrome P450 enzymes
DDI	Drug-Drug Interactions
eCRF	electronic Case Report Form
ECG	Electrocardiography
ЕоТ	End of Treatment
EMA	European Medicines Agency
eNOS	Endothelial nitric oxide synthase
ERA	Endothelin receptor antagonist
EU	European Union
FSH	Follicle-stimulating Hormone
FU	Follow-up
GCP	Good Clinical Practice
gGT	Gamma Glutamyl Transferase
GLP-1	Glucagon-Like Peptide-1
GMP	Good Manufacturing Practise
Hb	Haemoglobin
HBsAg	Hepatitis B virus s-Antigen
HCG	Human Chorionic Gonadotropin
HCVAb	Hepatitis C virus antibodies

Clinical Trial Protocol

Vicore Pharma ABVersion: 2.0Trial ID: VP-C21-013Date: 03-MAR-2023

HIV	Human Immunodeficiency Virus
HDL	High-density Lipoprotein
hs-CRP	high-sensitivity C-Reactive Protein
IB	Investigator's Brochure
ICH	International Conference on Harmonization
IEC	Independent Ethics Committee
IMP	Investigational Medicinal Product
IPF	Idiopathic Pulmonary Fibrosis
IUD	Intrauterine device
IUS	Intrauterine hormone-releasing system
LD	Lactate dehydrogenase
LDL	Low-density Lipoprotein
LFT	Liver Function Test
MDR1	Multi-Drug Resistance Protein 1
MedDRA	Medical Dictionary for Regulatory Activities
NO	Nitric oxide
NOAEL	No Observed Adverse Effect Level
PD	Pharmacodynamic
PK	Pharmacokinetic
PPAR _V	Peroxisome Proliferator-Activated Receptor-gamma
OAT3	Organic Anion Transporter 3
OATP1B1	Organic Anion Transporting Polypeptide 1B
QTcF	QT interval with Fridericia's correction
RAS	Renin-Angiotensin System
RHI	Reactive Hyperemia Index
RP	Raynaud's Phenomenon
SAE	Serious Adverse Event
SAP	Statistical Analysis Plan
SAS	Safety Analysis Set
SLC	Solute Carrier
SSc	Systemic Sclerosis
SOP	Standard Operating Procedure
SUSAR	Suspected Unexpected Serious Adverse Reaction
T2DM	Type 2 Diabetes Mellitus
TSH	Thyroid Stimulating Hormone
WHO	World Health Organization
WHODrug	WHO Drug Dictionary
WOCBP	Women of Childbearing Potential
